#### Exclusion Criteria:

• History of cardiovascular disease such as myocardial infarction, stroke, heart failure with or without LV ejection fraction <40%, cardiomyopathy, valvular heart disease,

cardiomyopathy, heart transplantation, Type 2 diabetes and Type 1 diabetes

- Smoking or history of smoking within past one year
- History of gastric ulcers, bleeding disorders, dyspepsia, severe gastroesophageal reflux disease (GERD), or metabolic acidosis
- History of asthma or lung disease (chronic obstructive pulomonary disease, COPD)
- Abnormal resting 12-lead ECG (e.g., evidence of myocardial infarction, left ventricular hypertrophy, left-bundle branch block, 2nd or 3rd degree AV block, atrial fibrillation/flutter)
- Serious neurologic disorders including seizures
- History of renal failure, dialysis or kidney transplant
- Serum creatinine > 2.2 mg/dL, or hepatic enzyme concentrations > 3 times the upper limit of normal
- History of HIV infection, hepatic cirrhosis, other preexisting liver disease, or positive HIV, Hepatitis B or C test at screening.
- Use of any investigational product or investigational medical device within 30 days prior to screening, or requirement for any investigational agent prior to completion of all scheduled study assessments.
- History of recent chicken pox, shingles or influenza (ie., risk of Reye's syndrome) Recent flu-like symptoms within the past 2 weeks
- Pregnant or breastfeeding at screening, or planning to become pregnant (self or partner) at any time during the study. A urinary pregnancy test will be done on all females. If test is positive, the subject will be excluded.
- Women with history of hormone replacement therapy within the past 6 months
- History of rheumatoid arthritis, Grave's disease, systemic lupus erythamatosis, and Wegener's granulomatosis;
- Taking medications for diabetes mellitus, kidney disease, liver disease, asthma, sepsis or seizure disorders:
- Taking lipid lowering (e.g., statins, niacin), glycemic control (e.g. metformin, insulin), anticoagulation, anti-seizure, anti-depression or antipsychotic agents
- History of co-morbid condition that would limit life expectancy to < 6 months.
- It is unknown if Salsalate is transferred in seminal fluid of men. However, it is recommended that proper protection such as a condom be used during intercourse during the study.
- Concomitant treatment with: aspirin, baby aspirin, indomethacin, naproxen (Aleve), acetaminophen (Tylenol), ibuprofen (Advil, Motrin), any other non-steroidal anti-inflammatory drugs; cox-2 inhibitors (Celebrex, Vioxx, etc); allopurinol (Zyloprim, Lopurin, Alopurin; coumadin (Wafarin), enoxaparin (Lovenox); clopidogrel (Plavix); dypyridamole (Persantine); heparin; diabetic medications (Metformin, glyburide, insulin, etc), TZDs (Avandia, Rezulin, Actos); corticosteroids (prednisone); methotrexate, infliximib (Remicade), etaneracept (Enbrel); levothyroxine (Levoxyl, Synthroid, Levoxyl, Unithroid); Levodopa; Phosphodiesterase (PDE) 5 inhibitors (e.g., Viagra®, Cialis®, Levitra®, or Revatio®); PDE 3 inhibitors (e.g., cilostazol, milrinone, or vesnarinone); lithium
- May participate if use of the following medications are discontinued 2 weeks prior to participation: salicylate medications, aspirin, antioxidants, herbal supplements, vitamins, omega-3 fatty acids; cox-2 inhibitors (Celebrex, Vioxx, etc)
- May participate if no use of the following medications in the 48 hours prior to experimental visits: naproxen (Aleve), acetaminophen (Tylenol), ibuprofen (Advil, Motrin), other any non-steroidal anti-inflammatory drugs
- Vulnerable populations (prisoners, etc.) are not included in this study because we are studying healthy middle-aged/older adults.
- Any condition that, in the view of the PI, places the subject at high risk of poor treatment compliance or of not completing the study.
- Hemoglobin <12 mg/dl for men; < 10 mg/dl for women
- History of alcohol abuse or >10 alcoholic units per week (1 unit= 1 beer, 1 glass of wine, 1 mixed cocktail containing 1 oz alcohol)
- Low platelets (<100,000 cu mm)
- On weight loss drugs (e.g., Xenical (orilistat), Meridia (sibutramine), Acutrim

(phenylpropanol-amine), or similar over-the-counter medications) within 3 months of screenina

Any surgery within 30 days of screening

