# VII.B.2 Does this project involve a drug washout (asking subject to stop taking any drugs s/he is currently taking)? Yes

### VII.B.3 Describe the management plan, including when you would stop the subject's participation in the event the subject worsens during the washout period.

If subjects are on salicylate medications, aspirin, antioxidants, herbal supplements, vitamins, omega-3-fatty acids, they may be in the study but will be asked during the consenting process to go off of these medications for 2 weeks before participating. If subjects are unwilling or medically unable to go off these drugs for the 2 weeks and during the course of the study, they will be ineligible to participate in the study and not consented. If they are willing to go through the 2 week washout, they can sign the consent during visit 1 but will have the Visit 1 procedures rescheduled to be completed in 2 weeks. If the subject is unclear if they can medically go off of the medications they will be required to contact their personal physician to confirm they can go off any of the prescription medications listed above for the study duration.

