#### Visit 1 (3.5 hours): Consent and Screening

- a. Explanation of the study; reading and signing of written informed consent b. If subject consents but requires a 2-week washout for aspirin, salicylate, NSAID, vitamin, supplements, they will be scheduled to complete the Visit 1 in 2 weeks. If subject consents and no washout is needed, screening tests will be performed same day to determine eligibility by the following:
- i. Research staff will obtain resting vitals (blood pressure, heart rate)
- ii. Research staff will obtain anthropometrics including weight, height, waist and hip circumference with tape measure.
- iii. Research staff will obtain resting 12-lead ECG
- iv. Subject will fill out the Demographics and Health History survey, and the Modified Activity Questionnaire (MAQ)
- v. Research nurse or trained staff will obtain venous blood draw using butterfly needle for UIHC pathology labs:
- Creatinine, Lipid panel, TSH(4.5 ml blood- 1 light green PST tube)
- Complete blood count(4.5 ml blood- 1 lavender tube)
- Subject will undergo oral glucose tolerance test (OGTT): Subject will consume a beverage containing 75 grams of glucose. Blood samples will be collected at timed intervals of baseline, 1 hour and 2 hours after consuming beverage for glucose and insulin. Total blood collected for insulin and glucose for OGTT: 13.5 ml blood (4.5ml x 3 PST tubes).
- TOTAL blood collected for Visit 1: 22.5 ml (1.5 Tablespoons)

- Visit 2 (2 hours): Dietary food record, cerebral blood flow velocity
- a. Meet with CRU bionutritionist for instruction on 3-day dietary record to return on visit 3
- b. Middle cerebral artery blood flow velocity using transcranial dopper during the following protocol to measure cerebral vasoreactivity to hypercapnia:
- -After 3 min of normal breathing, subjects will perform 2, 30 second breathholds sparated by 3 min.
- -Next, After 3 min of room air breathing, 3 min of breathin 2%CO2, 3 min of breathing 4%CO2 (balanced with 21%O2 and N) will be performed followed by 3 min of room air breathing.
- c. Subject will be instrumented with 24 hour blood pressure monitor to wear home for 24 hours. Subject will return it to the investigators when come in for Visit 3. There is no long term follow up.
- Visit 3 (3 hours): 1st Baseline experimental visit (Blood, Endothelial cells, FMD, PWV and Retina scan)
- a. Subject arrives at the CRU between 7-10 am after overnight 8 hour fast

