Heart attack or stroke: Because Salsalate is an NSAID, people who take NSAIDs (other than aspirin) may have a higher risk of having a heart attack or a stroke than people who do not take these medications. These events may happen without warning and may cause death. This risk may be higher for people who take NSAIDs for a long time and in those who have cardiovascular disease. There is no reported increased risk of heart attack or stroke in individuals on Salsalate so it cannot be determined what the exact risk (if any) is f Salsalate at the dose and duration in this study. Subjects are instructed to get emergency medical help right away if they experience any of the following symptoms during the study: chest pain, shortness of breath, weakness in one part or side of the body, or slurred speech.

Gastrointestinal bleeding: NSAIDs such as salsalate may cause ulcers, bleeding, or holes in the stomach or intestine. These problems may develop at any time during treatment, may happen without warning symptoms, and may cause death. The risk may be higher for people who take NSAIDs for a long time, are older in age, have poor health, smoke, or drink large amounts of alcohol or are on the following medications: anticoagulants ('blood thinners') such as warfarin (Coumadin); aspirin; other NSAIDS such as ibuprofen (Advil, Motrin) and naproxen (Aleve, Naprosyn); or oral steroids such as dexamethasone (Decadron, Dexone), methylprednisolone (Medrol), and prednisone (Deltasone). Also tell the research team if you have or have ever had ulcers, bleeding in your stomach or intestines, or other bleeding disorders. All of these medication are exclusion criteria in our study. Subjects are instructed to stop taking salsalate and call the study doctor if they experience any of the following during the study: severe stomach pain or heartburn, vomiting a substance that is bloody or looks like coffee grounds, blood in the stool, or black and tarry stools.

Risk of Reye's syndrome: If the subject has a recent history of a viral infection such as chickenpox or influenza they will not be allowed to participate because of the risk of developing Reye's syndrome (potentially fatal disease associated with viral illness and salicylate/aspirin use). If he subject has had recent flu-like symptoms you will be required to wait 2 weeks without any flu symptoms before participating.

Forearm blood flow test drugs:

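### Non-aspirin NSAIDs are excluded in one place, admitted with 48 hours' abstinence in another and washed out for 2 weeks in a third, so use during treatment is not settled and the bleeding-risk statement is contradicted for these drugs

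*Combined protocol and SAP*

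**What the plan says.** Four places in the combined document bear on non-aspirin NSAIDs.

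- **VI.13, Exclusion Criteria, concomitant treatment.** The excluded drugs include "naproxen (Aleve), acetaminophen (Tylenol), ibuprofen (Advil, Motrin), any other non-steroidal anti-inflammatory drugs; cox-2 inhibitors (Celebrex, Vioxx, etc").
- **VI.13, the next two items.** The first lets users of certain drugs in after a 2-week stop: "May participate if use of the following medications are discontinued 2 weeks prior to participation: salicylate medications, aspirin, antioxidants", continuing with supplements and cox-2 inhibitors. Naproxen, ibuprofen and other NSAIDs are not on that list. The second names naproxen, acetaminophen, ibuprofen and other NSAIDs and sets a shorter condition: "May participate if no use of the following medications in the 48 hours prior to experimental visits".
- **VII.E.6, Visit 1, step b.** Visit 1 is rescheduled when a consenting subject "requires a 2-week washout for aspirin, salicylate, NSAID, vitamin, supplements".
- **VIII.1, gastrointestinal bleeding.** The paragraph says bleeding risk on NSAIDs such as salsalate may be higher in people who also take anticoagulants, aspirin, other NSAIDs (ibuprofen and naproxen are named) or oral steroids. It then states: "All of these medication are exclusion criteria in our study".

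The washout plan (VII.B.3) is also relevant. Its list is "If subjects are on salicylate medications, aspirin, antioxidants, herbal supplements, vitamins, omega-3-fatty acids, they may be in the study" after a 2-week stop, and it turns away anyone "unwilling or medically unable to go off these drugs for the 2 weeks and during the course of the study". That abstinence through the study attaches to its own list, which contains no non-salicylate NSAID.

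**The concern.** A coordinator screening an ibuprofen user could exclude the subject, defer for 2 weeks, or ask for 48 hours without the drug, and could point to the text for each. VII.B.11 says there is no separate written protocol, so nothing else settles the matter.

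Two things are at stake. The first is safety. VIII.1 itself classes salsalate as an NSAID and says that adding another NSAID may raise bleeding risk. It offers exclusion as the safeguard, yet the 48-hour item lets the two be combined between visits. The second is the treatment contrast. The hypotheses in I.5 concern chronic inflammation inhibition, and a placebo subject who takes an NSAID between visits may be receiving some of it.

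Neither would show up in the data as planned. Visit 5 takes a salicylate level, blood pressure, heart rate and a side-effect survey. Visits 6 and 7 add outcome measurements and laboratory tests. The text describes no question about NSAID use at any of these visits, VIII.4 does not list it among the data for safety review, and XI.1 plans no analysis of it.

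**Working it through.** The plan gives no figure on this point to reproduce. The main check is to compare the text drug by drug.

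| Drug | Concomitant exclusion (VI.13) | 2-week item (VI.13) | 48-hour item (VI.13) | Washout plan (VII.B.3) | Visit 1 washout (VII.E.6) | Bleeding text (VIII.1) |
|---|---|---|---|---|---|---|
| Naproxen, ibuprofen, other NSAIDs | excluded | not listed | admitted | not listed | 2 weeks | said to be excluded |
| Aspirin | excluded | 2 weeks | not listed | 2 weeks and through the study | 2 weeks | said to be excluded |
| Anticoagulants, oral steroids | excluded | not listed | not listed | not listed | not listed | said to be excluded |

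- **Row 1 cannot be satisfied as a whole.** A 48-hour allowance is incompatible with a 2-week washout and with the statement that the drugs are exclusions.
- **Row 2 is consistent on use during the study.** Aspirin users may enter after 2 weeks off, but VII.B.3 keeps them off it throughout.
- **Row 3 has no conflict.**
- **The two 2-week lists agree about non-aspirin NSAIDs.** VI.13 and VII.B.3 both leave them out, so VII.B.3 is not a further contradiction. They differ on cox-2 inhibitors, which only VI.13 lists. Cox-2 inhibitors could also be read into the 48-hour item's wording on other NSAIDs.

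**Time left open by the 48-hour item.** First dose is at Visit 4 (Day 0) and Visit 6 falls on Day 26–34 (VII.E.6). Open share = (Visit 6 day − 2) / Visit 6 day.

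- Visit 6 on Day 26: 24/26 = 92%.
- Visit 6 on Day 34: 32/34 = 94%.

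Visit 5 (about Day 14) is described in VIII.2 as a safety visit. If it were counted as experimental, 2 more days would close: 22/26 = 85% and 30/34 = 88%.

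**Illustration of the effect on the contrast.** Let f be the share of placebo subjects using NSAIDs and g the fraction of the salsalate effect each user gains. Assume no change on salsalate. The standardised difference becomes d × (1 − f·g), with d = 1.06 from XI.2. Power below is for a two-sided t-test at 0.05 (sidedness is not stated in XI.2, so two-sided is assumed) with 20 v 10 subjects.

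| g | f = 0 | f = 10% | f = 20% | f = 30% |
|---|---|---|---|---|
| 0 | 75% | 75% | 75% | 75% |
| 0.25 | 75% | 73% | 71% | 69% |
| 1 | 75% | 66% | 56% | 46% |

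For example, f = 30% and g = 1 gives d = 1.06 × 0.70 = 0.74. The documents supply neither f nor g. The answer runs from no loss to a large one, so the table shows only that the loss cannot be estimated. The 75% starting point reflects the 2:1 allocation and is a separate matter.

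**The case against.** The strongest defence is that VI.13 is one rule with two exceptions: the concomitant-treatment item lists what is excluded, and the next two items say when stopping is enough, 2 weeks for some drugs and 48 hours for others. One could add that concomitant treatment means regular use and the 48-hour item means occasional use. Read this way, VI.13 is coherent and the omission of NSAIDs from VII.B.3 follows from it.

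Much of that stands, but it does not remove the problem. The documents draw no line between regular and occasional use. Visit 1 and the bleeding paragraph remain contradicted, and non-salicylate NSAIDs could still be taken alongside salsalate between visits. VI.13 also shows that a full-period rule could be written: its inclusion criteria require vitamins C and E to stop 2 weeks before and throughout treatment. No equivalent covers these NSAIDs.

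Three stronger readings are tempting and are not supported:

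- **That the bleeding safeguard fails altogether.** It fails only for non-aspirin NSAIDs. The exclusions for ulcers, bleeding disorders, dyspepsia, severe reflux disease, low platelets and low hemoglobin are untouched, as is the instruction to stop and call if bleeding symptoms occur.
- **That this is mainly contamination of the placebo arm.** The 48-hour item applies equally to both arms.
- **That the trial loses a known amount of power.** That needs a use rate and a salsalate-like benefit from other NSAIDs. The rationale in I.6 concerns salsalate's action on the IKKB/NFkappaB pathway, and nothing says ibuprofen or naproxen share it or improve pulse wave velocity.

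A reader might also infer that baselines already mix 48-hour and 2-week abstainers. The wording makes that possible, but nothing shows that it happens.

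**Conclusion.** The concern holds for naproxen, ibuprofen and other non-aspirin NSAIDs. VI.13 can be made coherent only by a reading that leaves Visit 1 (VII.E.6) and the bleeding paragraph (VIII.1) contradicted. It goes beyond a missing detail, because the text as it stands allows a drug combination that the risk section tells the reader is excluded.

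The size is a matter of opportunity. If the 48-hour item governs, NSAIDs are open to both arms for 92–94% of the time from first dose to Visit 6 (85–88% if Visit 5 counts as experimental). How many subjects would use them is unknown, and so is any effect on the outcomes. With 10 placebo subjects planned, each user is a tenth of the comparator, but the direction and amount of bias cannot be fixed from the documents.

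This should be corrected. It does not on its own invalidate the design.

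**What to change.** Reconcile VI.13, Visit 1 in VII.E.6 and the bleeding paragraph in VIII.1, with VII.B.3 as needed, into one rule for non-aspirin NSAIDs. The rule should state separately what applies before baseline and what applies from first dose to Visit 7, and whether regular and occasional use are treated differently. It should also place cox-2 inhibitors and acetaminophen, which are caught in the same lists. Then make the bleeding statement agree with the rule. Which rule applies is for the investigators to decide.

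At Visits 5, 6 and 7, ask about and record any NSAID use since the previous visit (drug, dates, most recent intake), and report it by arm. This makes any effect on the contrast, and any combined exposure on salsalate, visible afterwards.

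The cost is a wording amendment, with the consent text checked to match, and one question at visits that already take place. No change to sample size or to the primary analysis is needed.

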- d. Subject escorted to the CRU Human Cardiovascular Research Lab and a physician or research staff trained in microneurography will insert needle into peroneal nerve for measurement of muscle sympathetic nerve activity
- e. Subject will be instrumented with 24 hour blood pressure monitor to wear home for 24 hours. Subject will return it to the investigators when come in for Visit 7. There is no long term follow up.

Total blood collected for visit 6: 68 (~4.5 Tablespoons)

Visit 7 (3 hours) Between Day 27-35: Post-experimental visit #2

- a. Subject will take morning dose of Salsalate/placebo return to CRU on Day 27 or 28 for venous blood sample to measure serum salicylate, AST/ALT and creatinine (0.5 ml blood)
- b. All measurements from Visit 4 will be repeated
- c. Blood draw for salicylate, insulin, lipid panel, creatinine, ALT/AST (1  $\times$  4.5 ml lt green PST tube)
- d. Total blood collected for visit 7: 4.5 ml ( $\sim$ 1/3 tablespoon)

GRAND TOTAL Blood drawn over course of study: 172 ml (~11.5 tablespoons)

Screening Methods.

- a) Blood pressure, ECG. Subject will undergo resting BP in a private CRU exam room after 15 minutes of rest. BP will be measured in supine position in triplicate separated by 2 min with an automated oscillometric BP machine under quiet, comfortable laboratory conditions. All BPs throughout study will be performed in this identical manner. A resting supine 12-lead ECG will be recorded by placing 10 electrodes on chest and recording the ECG.
- b) History and Physical exam. Prior to the experimental visit (Visit 3), subjects will undergo a complete medical history and physical examination by [name] or a CRU nurse practitioner.
- c) Blood chemistries: After passing the physical exam standard blood chemistry analysis will be obtained under fasting conditions including a basic metabolic panel, lipid panel, HbA1C, complete blood count, TSH and FSH (for women only).

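### The haemoglobin exclusion limits carry an implausible unit (mg/dl), so as written the criterion can exclude no one; the sponsor should confirm and correct the line

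*Combined protocol and SAP*

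**What the plan says.** Section VI.13, Exclusion Criteria, lists "Hemoglobin <12 mg/dl for men; < 10 mg/dl for women". This is the only haemoglobin limit in the documents. No section uses g/dl or names anaemia as a criterion.

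Haemoglobin would be read from the complete blood count. VII.D.26 lists that test as a screening procedure, VII.E.6 places it at Visit 1 ("Complete blood count(4.5 ml blood- 1 lavender tube"), and the Screening Methods part of VII.E.6 repeats it. The blood tests listed for later visits do not include it.

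Nearby criteria also bear on bleeding. VI.13 excludes "History of gastric ulcers, bleeding disorders, dyspepsia, severe gastroesophageal reflux disease (GERD), or metabolic acidosis" and, separately, "Low platelets (<100,000 cu mm"). It also lists anticoagulants, aspirin and other NSAIDs. The risk section (VIII.1) classes the study drug as an NSAID ("Because Salsalate is an NSAID") and states that "NSAIDs such as salsalate may cause ulcers, bleeding, or holes in the stomach or intestine".

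**The concern.** An exclusion limit is a decision rule: a screening result is compared with it, and the person is admitted or not. If the limit lies below any value the test can return, the rule never acts. A screener applying the text literally would pass everyone on this item. A screener who reads the numerals in g/dl would exclude some people, but on a limit that the approved text does not state. In either case the written rule and the working rule differ, and eligibility on this item cannot be audited against the document.

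The documents do not say why the criterion is there. The stated gastrointestinal bleeding risk and the repeated blood sampling are plausible reasons for wanting it to work, but that link is an inference.

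**Working it through.** **Inputs.** Limits of 12 mg/dl (men) and 10 mg/dl (women), from VI.13. Conversion: 1 g = 1,000 mg. The documents give no haemoglobin range, so I assume 3 to 13 g/dl, meant to run from severe anaemia to near-normal.

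**Step 1: the limits as written.**
- Men: 12 / 1,000 = 0.012 g/dl.
- Women: 10 / 1,000 = 0.010 g/dl.

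**Step 2: assumed results against those limits.** The range 3 to 13 g/dl is 3,000 to 13,000 mg/dl.
- Men: 3,000 / 12 = 250 and 13,000 / 12 = 1,083 times the limit.
- Women: 3,000 / 10 = 300 and 13,000 / 10 = 1,300 times the limit.

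No value in the range falls below either limit. The result hardly depends on the assumed range, because any haemoglobin above 0.012 g/dl passes for both sexes.

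**Step 3: the effect of the unit alone.** With the same numerals in g/dl, the limits become 12,000 and 10,000 mg/dl, 1,000 times those written. Of test values 3, 5, 7, 9, 11 and 13 g/dl:

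| | Excluded as written | Excluded if the unit were g/dl |
|---|---|---|
| Men | none | 3, 5, 7, 9, 11 |
| Women | none | 3, 5, 7, 9 |

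This illustrates the unit only. It does not say what the limits ought to be.

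**Step 4: does anything else correct the line?**
- Elsewhere mg/dl can be taken at face value: creatinine 2.2 and glucose 100-126 (VI.13), salicylate 30 (VIII.2). Nothing signals a different meaning here.
- VII.B.11 answers that no separate written protocol will be submitted.
- The healthy-subject inclusion criterion names renal, liver and thyroid limits, but no haemoglobin value. The investigator-discretion exclusion concerns compliance and completion.
- The phone screen (VII.D.20) and the chart-review list (VII.D.2) do not ask about anaemia.
- The bloods listed for Visits 3, 5, 6 and 7 and the four-week chemistries (VII.E.6) contain no complete blood count. The laboratory data named in the safety report (VIII.4) are salicylate, creatinine and ALT/AST.

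**Step 5: the sampling volume.** VII.E.6 states "GRAND TOTAL Blood drawn over course of study: 172 ml". The stated visit totals reproduce it: 22.5 + 68 + 9 + 68 + 4.5 = 172 ml (Visits 1, 3, 5, 6, 7). The 10 non-prediabetic controls do not attend Visits 5 to 7, so their stated total is 22.5 + 68 = 90.5 ml.

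**The case against.** The strongest reply is that the slip is too conspicuous to mislead. Anyone comparing a blood-count result with 12 or 10 would see the mismatch and read g/dl. A wrong but believable limit would be more dangerous. This largely stands, and it is why the practical effect may be small. It does not make the written rule enforceable.

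The second reply is that subjects have other protection. Ulcer history, bleeding disorders, low platelets, anticoagulants and concomitant NSAIDs are addressed in VI.13. The phone screen asks about gastrointestinal bleeding, ulcers, bleeding disorders and blood thinners. Subjects must be judged healthy on history and examination, and VIII.1 tells them to stop the drug and call if signs of bleeding appear. This stands too. A reader might infer from the faulty line that the trial has no bleeding safeguards, and the documents contradict that. What remains is narrower: none of these provisions sets a haemoglobin limit.

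Third, declining an anaemic volunteer does that person no safety harm, and the general health requirement could support the same decision. That is fair. It makes the departure from the approved wording a documentation matter.

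Finally, a reader might apply the drug risk and the 172 ml to everyone. Of 40 planned subjects, 20 are assigned salsalate and 10 placebo, while 10 controls receive neither and give 90.5 ml by the stated totals.

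**Conclusion.** The point holds as a unit error in an operative eligibility threshold. As written, the criterion can exclude no one. If the same numerals were meant in g/dl, the written limits are too low by a factor of 1,000. The first statement needs only that real haemoglobin values exceed 0.012 g/dl; the second assumes that the numerals are as intended, which the documents do not confirm.

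A reader might go further and infer that anaemic subjects would in fact be enrolled, or were put at risk. The documents do not support that. They give no haemoglobin distribution and no account of how screeners apply the line, and the likely reading by staff is g/dl. How many subjects would be affected in practice is unknown and may be none.

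No calculation in the plan is wrong on this account; sample size, power and the planned analyses are untouched. The line still merits correction, because it is the only haemoglobin rule and the listed tests offer no later check.

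**What to change.** Ask the sponsor to confirm both the intended numerals and the intended unit of the haemoglobin exclusion in VI.13, and to correct that line accordingly through the usual amendment route. Any screening form or checklist that copies the line should be brought into agreement with it.

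The cost is a correction to one line. The complete blood count is already drawn at screening, so no test, visit, procedure or analysis has to be added or changed.
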